7. SUBJECTS

7.1. Subject Population

Eligible test subjects will be 18-45 years of age who currently have mild to moderate symptoms of dry eye as defined by a screening SANDE score of 20 to 55 inclusive (equivalent to OSDI score of 12 to 32).²

A total of 70 subjects at one site will be enrolled. Both eyes of a subject must be enrolled. Subjects must meet the inclusion criteria. Prior to enrollment, subjects will be provided information on the study and asked to sign a patient information and consent form to participate. The patient information and consent form will be approved by an appropriate ethics committee.

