8.3. Method of Assigning Subjects to Treatment Arms

Subjects will be assigned to Systane Complete Multi-Dose PF or the Walgreen's Lubricant Balance treatment groups in a 1:1 ratio using the method of randomly permuted blocks.

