9.2.1. Recruitment

At the recruitment visit, subjects will be consented, qualified for the study (compared with inclusion/exclusion criteria), and assigned a study ID/subject number. Subject numbers will be assigned sequentially at each site in the order of enrollment.

A medical history will be taken and exams will include the tests described below:

- slit lamp exam including evaluation of staining,
- non-invasive tear breakup time,
- SANDE questionnaire.

In addition, all site-specific, routine, usual standard of care measures should be undertaken.

Measurements should be made as described in section 9.3 below.

9.2.2. Follow-Up Visit 1

Exams will include the tests described below:

- SANDE questionnaire,
- compliance check.

In addition, all site-specific, routine, usual standard of care measures should be undertaken.

Any adverse events/serious adverse events (AEs/ SAEs) occurring during surgery will be noted at this visit. Any other problems during surgery and comments regarding surgery will be documented.

9.2.3. Follow-Up Visit 2

Exams will include the tests described below:

- slit lamp exam including evaluation of staining,
- non-invasive tear breakup time,

- SANDE questionnaire,
- compliance check.

In addition, all site-specific, routine, usual standard of care measures should be undertaken.

Any adverse events/serious adverse events (AEs/ SAEs) occurring during surgery will be noted at this visit. Any other problems during surgery and comments regarding surgery will be documented.

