11. SAMPLE SIZE JUSTIFICATION

Assuming a difference in means between groups of 7 (SANDE) and a pooled standard deviation of 6, the study would require a sample size of 16 subjects for each group (total sample size of 32 subjects) to achieve a power of 90% and a level significance of 5%. To increase the study power and account for dropout, the sample size is being increased to 70 subjects (35 in each arm) to thoroughly characterize the performance of the drops.

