13. QUALITY COMPLAINTS AND ADVERSE EVENTS

All subjects will be monitored for adverse events over the course of the study. A place to record any adverse event is included on each case report form.

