18.2. Patient Discontinuation

Each study patient may voluntarily discontinue the study at any time they choose. Study patients who cannot complete the study for administrative reasons (e.g., non-compliance, failure to meet visit schedule, etc.) will be discontinued from the study. Study patients discontinued during the enrollment phase (prior to surgery) of the study will be replaced.

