18.3. Patient Termination

A study patient will be terminated if the study patient develops any severe adverse event that may be related to the study. A study patient will receive appropriate treatment at the discretion of the investigator. Notification of termination will be clearly documented. These study patients are considered to have completed the study and will not be replaced.

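### Does tying subject replacement to a surgery that this eyedrop trial does not have leave the number randomised open?

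*Combined protocol and SAP*

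**What the plan says.** Section 18.2 gives the only replacement rule: "Study patients discontinued during the enrollment phase (prior to surgery) of the study will be replaced". Section 18.3 settles one group separately, those terminated for a severe adverse event that may be related to the study: "These study patients are considered to have completed the study and will not be replaced".

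On numbers, section 7.1 states: "A total of 70 subjects at one site will be enrolled". Section 11 derives 32 subjects and then explains the larger figure: "To increase the study power and account for dropout, the sample size is being increased to 70 subjects", that is, 35 per arm.

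On timing, section 8.3 says only that allocation is "in a 1:1 ratio using the method of randomly permuted blocks". Section 9.2.1 describes Day 0: "At the recruitment visit, subjects will be consented, qualified for the study (compared with inclusion/exclusion criteria), and assigned a study ID/subject number". Neither gives a moment for randomisation, and it is not among the nine activities in Table 15.1.

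Sections 9.2.2 and 9.2.3, the two follow-up visits, both carry this sentence: "Any adverse events/serious adverse events (AEs/ SAEs) occurring during surgery will be noted at this visit". Each follows it with a request to document problems and comments about surgery. Section 13, by contrast, covers adverse events over the whole study and adds: "A place to record any adverse event is included on each case report form".

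**The concern.** The rule in 18.2 is an instruction with a cut-off, and the cut-off is an event that cannot occur. Section 8.1 describes a comparison of two eyedrops, and 7.3 excludes anyone with a history of ocular surgery. The term enrolment phase is not defined. Two readings are then possible.

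- **Narrow:** only subjects lost around consent and qualification on Day 0 are replaced.
- **Broad:** because nobody has surgery, every discontinuation precedes it, and everyone except an 18.3 termination is replaced. Withdrawals, losses to follow-up, non-compliance and missed visits would all count.

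On the broad reading the number randomised could exceed 70. Sections 10.1 and 10.2 restrict efficacy to completers and the per-protocol population, so replacing treated dropouts would also change who enters the primary comparison. If the choice were made case by case after treatment began, that would be discretion the plan does not control. The surgery wording at the follow-up visits raises a smaller worry, that staff might take the visit-level adverse event instruction as not applicable.

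**Working it through.** **1. The plan's own sample size.** Inputs from section 11: difference 7, pooled SD 6, power 90%, 5% significance (sidedness not stated; two-sided reproduces the figure). Normal approximation:

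n per arm = 2 × SD² × (1.960 + 1.282)² / difference² = 2 × 36 × 10.51 / 49 = 15.4, rounded up to 16, or 32 in total.

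This matches section 11. A one-sided 5% test would give 13 per arm, which does not match. With the exact noncentral t, 16 per arm gives 89.1% power and 17 gives 90.9%.

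**2. Does power depend on the replacement rule?** Two-sample t-test, two-sided 5%, noncentrality = difference / (SD × √(2/n)). The plan gives no dropout rate; 28 per arm illustrates 20% loss (70 × 0.80 = 56 completers).

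| SD | 35 per arm | 28 per arm |
|---|---|---|
| 6 (plan) | 99.8% | 99.0% |
| 8 (assumed) | 95.0% | 89.5% |
| 10 (assumed) | 82.3% | 73.0% |

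At SD 6 and 35 per arm, for example, noncentrality = 7 / (6 × √(2/35)) = 4.88. On the plan's inputs, losing seven per arm costs less than one percentage point. From 70 subjects, 70 − 32 = 38 (54%) could be lost before reaching the 32 that section 11 takes as sufficient.

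**3. How far could the number randomised move?** Without replacement, 70. If dropouts were replaced until 70 completed, the number is 70 / (1 − dropout rate), rounded up:

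- 5% dropout (assumed): 70 / 0.95, so 74
- 10%: 70 / 0.90, so 78
- 15%: 70 / 0.85, so 83
- 20%: 70 / 0.80, so 88

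**4. Which reading does the text support?**

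- 18.2 confines replacement to an enrolment phase. A rule covering every dropout would need no such phase.
- 9.1 and 9.2.1 put enrolment at consent and qualification on Day 0.
- 7.1 gives 70 as the number enrolled, and section 11 says that number already absorbs dropout. The broad reading conflicts with both.
- 9.2.4 and 9.5 deal with premature exit and discontinuation at length and never mention replacement.
- Visit 1 is Day 0, Visit 3 is Day 14 (±2 days), and the primary endpoint is change after two weeks on the drop. Assignment must therefore fall at about Day 0, even though no row in Table 15.1 says so.

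With the stray parenthesis struck out, what remains is replacement of early enrolment losses only.

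**5. Adverse events.** Section 13.2 has the investigator ask about problems at each visit. Section 13.3 requires all untoward occurrences after consent to be documented. Table 15.1 marks adverse event monitoring at Visits 2 and 3. None of these depends on the surgery sentences.

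**The case for a change.** The strongest case for a change is that 18.2 is operative text and nothing overrides it in so many words. Section 11's dropout allowance favours no replacement after randomisation but does not state it. Section 18.3 settles only one kind of loss. Because efficacy is analysed in completers, a loose replacement rule could affect who is compared as well as how many. A change of wording and one table row would cost little, and if the SD proved larger than 6 the number of completers would matter more: at an assumed SD of 10, going from 35 to 28 per arm lowers power from 82.3% to 73.0%.

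Much of this stands as description. The cut-off is not explicit, the surgery wording is wrong in three places (18.2, 9.2.2 and 9.2.3), and whether 70 means enrolled or randomised is not spelled out. What does not stand is the step to consequence. The broad reading contradicts 7.1 and section 11, so a site would have to set both aside to follow it. No mechanism was shown by which either reading would bias the treatment comparison or alter the type I error. The restriction to completers applies whatever 18.2 says. The larger SDs have no source in the plan, and they bear on section 11's choice of SD rather than on the replacement rule.

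**Conclusion.** The wording is a clerical leftover, and the gap behind it is one that a site and its analyst would fill sensibly: replace subjects lost before treatment, do not replace those lost afterwards, and record adverse events under section 13. On the plan's inputs the choice of reading moves power by less than one point between 35 and 28 completers per arm (99.8% to 99.0%). The number randomised is 70 on the favoured reading; the 74 to 88 under full replacement rests on an assumed 5% to 20% dropout and on a reading that the rest of the document contradicts. Tidying the surgery references if the protocol is reissued would be good housekeeping, but it would change no analysis, result or conclusion.

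This rests on section 11's difference of 7 and SD of 6, a two-sided 5% test, and 70 being the number who enter the trial, as 7.1 and section 11 indicate.

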18.3. Patient Termination

A study patient will be terminated if the study patient develops any severe adverse event that may be related to the study. A study patient will receive appropriate treatment at the discretion of the investigator. Notification of termination will be clearly documented. These study patients are considered to have completed the study and will not be replaced.

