9.2.4. Exit Procedures

In the event of premature exit from the study, all study related examinations should be completed where possible. The Exit CRF should be completed, noting that the subject did not complete the study and the reason for premature study exit. If no premature exit from the study occurs, the Exit CRF should be completed at the end of Visit 3.

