9.5. Discontinued Subjects

Discontinued subjects are those who do not have an exit visit or who come into the office to be exited prior to the scheduled final study visit. Subjects may be discontinued from the study at any time if, in the opinion of the investigator, their continued participation in the study poses a risk to their health. The reasons for discontinuation include:

- a. Adverse event;
- b. Lost to follow-up;
- c. Subject decision unrelated to an adverse event;
- d. Protocol violation;
- e. Treatment failure;
- f. Other.

To ensure the safety of all subjects who discontinue prior to Visit 3, investigators should assess each subject and, if necessary, advise them of any therapies and/or medical procedures that might be needed to maintain their health. Any changes in medical health and/or use of concomitant medications should also be captured.

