10. ANALYSIS PLAN

10.1. Analysis Data Sets

All subjects who are enrolled in the study will be evaluated for safety. Efficacy analyses will be performed based on data from those eyes that complete the study.

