10.2. Statistical Methodology

Analysis will be done on the per protocol population. For monocular outcomes, analysis will be performed on the study eye that was determined by randomization.

Superiority of Systane COMPLETE relative to Walgreens will be established if the mean SANDE score is significantly lower in the Systane COMPLETE group vs. Walgreens group.

Demographics, baseline characteristics, efficacy endpoints, and adverse events will be summarized descriptively. Summaries of these variables will include sample size, as well as the mean, median, standard deviation, minimum and maximum.

Primary Endpoint: Dry eye symptom frequency and severity as measured by the SANDE questionnaire change after 2 weeks of QID use (subject level). Total scores will be compared using a two-sample t-test.

The step-down methodology will be used on the other endpoints in the following order:

- Comparing corneal and conjunctival staining in the study eye before and after 2 weeks of QID use of their assigned drop (eye level). The corneal and conjunctival staining scores will be totaled from the 5 evaluation zones for analysis. Total scores will be compared using a two-sample ttest.
- Comparing Non-invasive TBUT times of the study eye in the two arms of the study, before and after 2 weeks of QID use of their assigned drop (eye level). Time will be compared using a two-sample t-test.
- Dry eye symptom frequency and severity as measured by the SANDE questionnaire after 1 week of QID use (subject level). Total scores will be compared using a two-sample t-test.

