12.3.1 Intensity and Causality Assessments

For every adverse event and quality complaint, the investigator must assess the causality as Related or Not Related to the medical device under investigation. An assessment of causality will also be performed by the Medical Monitor utilizing the same definitions, as shown below:

Causality

- Related An adverse event or quality complaint classified as related may be either definitely related or possibly related where a direct cause and effect relationship with the medical device has not been demonstrated, but there is a reasonable possibility that the adverse event or quality complaint was caused by the medical device.
- Not Related An adverse event or quality complaint classified as not related may either be definitely unrelated or simply unlikely to be related (i.e., there are other more likely causes for the adverse event or quality complaint).

Where appropriate, the investigator must assess the intensity (severity) of the adverse event as mild, moderate, or severe based on medical judgment with consideration of any subjective symptom(s), as defined below:

Intensity (Severity)

Mild	An adverse event is mild if the subject is aware of but can easily
Moderate	An adverse event is moderate if the sign or symptom results in
	discomfort significant enough to cause interference with the subject's usual activities
Severe	An adverse event is severe if the sign or symptom is incapacitating and results in the subject's inability to work or engage in their usual activities.

The investigator must document any action taken (i.e., medication, intervention, or treatment plan) and outcome of the adverse event or quality complaint when applicable.

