15. STANDARD EVALUATION PROCEDURES

Table 15.1. Proposed Visits and Study Assessments

(visits are by patient, with both eyes tested)

Activity	Recruit- ment	Follow-Up	Follow-Up
	Visit 1	Visit 2	Visit 3
Informed Consent	Х		
Demographics	Х		
General Information: Medical History	Х		
Non-Invasive Tear Breakup Time	Х		Х
Slit Lamp Exam and Staining Evaluation	Х		Х
SANDE Questionnaire	Х	Х	Х
Compliance Check		Х	Х
Monitor for Adverse Events		Х	Х
Complete Exit Form ¹			X

¹ Complete Exit Form upon termination of subject participation, or at Visit 3, whichever occurs first.

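### Section 18.3 counts subjects terminated early for a severe, possibly related adverse event as completers, against 18.1, 9.2.4, 9.5 and 18.5, while 10.1 selects the efficacy set on completion

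*Combined protocol and SAP*

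**What the plan says.** Section 18.3 requires termination of a subject who develops a severe adverse event that may be related to the study, and then gives that subject's status: "These study patients are considered to have completed the study and will not be replaced".

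Other sections deal with the same subject when termination comes before Visit 3:

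- **18.1** defines completion as having completed Visit 3.
- **9.2.4**, on premature exit: "The Exit CRF should be completed, noting that the subject did not complete the study and the reason for premature study exit". It also asks for the assessments to be done: "In the event of premature exit from the study, all study related examinations should be completed where possible".
- **9.5** includes among discontinued subjects those "who come into the office to be exited prior to the scheduled final study visit", and adverse event is the first reason listed.
- **18.5** ends the study when every enrolled patient has either completed Visit 3 or been terminated, which makes these two different end states.
- **Table 15.1, footnote 1**, sets when the form is filled in: "Complete Exit Form upon termination of subject participation, or at Visit 3, whichever occurs first".

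The analysis plan then relies on completion. Section 10.1 states: "Efficacy analyses will be performed based on data from those eyes that complete the study". Section 10.2 adds that analysis is on the per protocol population and does not define it. The primary endpoint in 10.2 is SANDE change after 2 weeks, and Table 9.2-1 places Visit 3 at Day 14 ± 2 days.

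**The concern.** A subject terminated before Visit 3 has two opposite statuses. A site following 9.2.4 records that the subject did not complete; a data manager following 18.3 records that the subject did. Nothing in the protocol says which prevails, and 10.1 uses the same word to choose who enters the efficacy analysis.

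Two things could go wrong. First, a withdrawal for a severe, possibly treatment-related event could be presented as a completion. That information matters here because the introduction contrasts a preserved with a preservative-free drop and names the preservative as a cause of dryness and staining. Withdrawal for adverse events by arm is therefore of interest in its own right. Second, 9.2.4 means that an early-exit SANDE score may exist. If the subject counts as a completer, that score could be taken as the 2-week value. No section proposes this and none forbids it.

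A related but separate matter comes from 10.1 alone. Restricting efficacy to completers drops early withdrawals, and these may differ between arms in number and in symptoms.

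**Working it through.** **Step 1. Set the sections side by side for a subject terminated on, say, Day 5.**

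| Section | Status of the subject |
|---|---|
| 18.3 | Completed |
| 18.1 | Not completed (no Visit 3) |
| 9.2.4 | Not completed, reason recorded on the Exit CRF |
| 9.5 | Discontinued, adverse event |
| 18.5 | Terminated, as distinct from completed Visit 3 |
| Table 15.1 footnote | Exit Form due at termination; silent on status |

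The footnote shows only that termination can precede Visit 3. The conflict rests on the other sections. If the severe event is found at Visit 3 itself, the subject has completed on any reading and there is no conflict.

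**Step 2. Is the clause needed for replacement accounting?** No. The second half of the sentence in 18.3 already rules out replacement, and 18.2 replaces only subjects discontinued in the enrollment phase.

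**Step 3. Reproduce the plan's own figure.** Inputs from section 11: difference 7, SD 6, significance level 5% (two-sided assumed), power 90%. Normal approximation:

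n per group = 2 × (1.960 + 1.282)² × 6² / 7² = 15.4, rounded up to 16.

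This matches the stated 16 per group. The noncentral t distribution gives 89.1% power at 16 per group. The planned size is 35 per arm.

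**Step 4. Size in disposition.** One subject is 1/35 = 2.9% of an arm; two are 2/35 = 5.7%. Under 18.3 either could be shown as 0% discontinued for adverse events.

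**Step 5. Size in efficacy, only if an early-exit score were entered.** One subject whose change lies X points from the mean of the rest of the arm shifts the mean of 35 by X/35. The documents give no value for X; I assume 10 to 30.

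- X = 10: 10/35 = 0.29 points, 4.1% of the planned difference of 7
- X = 20: 20/35 = 0.57 points, 8.2%
- X = 30: 30/35 = 0.86 points, 12.2%

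For scale, the standard error of the difference at 35 per arm is 6 × √(2/35) = 1.43 points.

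**Step 6. Effect on power of leaving such subjects out.** Two-sample t-test, two-sided 5%, difference 7, SD 6, noncentral t:

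| Arms | Power |
|---|---|
| 35 v 35 | 0.9978 |
| 34 v 35 | 0.9976 |
| 33 v 35 | 0.9973 |
| 32 v 35 | 0.9969 |

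Power is not at issue.

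**The case against.** The strongest reply is that 18.3 is administrative. The sentence pairs completion with non-replacement and sits between the replacement rule in 18.2 and the end-of-study rule in 18.5. The reference to surgery in 18.2, in an eye-drop trial, suggests that the section was carried over from another protocol. On that view the clause was never meant to feed 10.1. This is plausible, but the text does not say so, and step 2 shows that the clause does no work for replacement.

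Three stronger readings are tempting, and the documents do not support them.

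- *A reader might infer that these withdrawals will be reported as 0%.* Section 10 plans no disposition table and does not say that discontinuation counts come from 18.3. The Exit CRF records non-completion with its reason, 18.3 itself requires termination to be documented, and adverse events are captured under 10.1, 13.3 and 13.5. The supported statement is that they could be reported as completers.
- *A reader might infer that 18.3 biases the primary comparison.* A subject terminated before the Visit 3 window has no scheduled 2-week value under either reading, so the t-test is the same unless an early-exit score is substituted. The undefined per protocol restriction in 10.2 is a further filter. The exclusion of such subjects comes from 10.1, not from 18.3.
- *A reader might take the Table 15.1 footnote as classifying these subjects as premature exits.* It only times the form.

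It can also be said that a supportive analysis using early scores relies on the same values that are a hazard in the primary analysis. The difference is that there they would be declared in advance, labelled and counted, not entered unmarked as 2-week values.

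**Conclusion.** The contradiction stands on the current text and is a stated rule that misclassifies, not a missing detail. Its practical size is small. Severe is a demanding grade in 12.3.1 ("An adverse event is severe if the sign or symptom is incapacitating"), and exposure is two weeks of lubricating drops, so few or no subjects are likely to be affected. The documents give no expected rate, so this is a judgement.

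Each affected subject is 2.9% of an arm in disposition. The 0.29 to 0.86 point shift in an arm mean depends on two assumptions: the size of the deviation, and the use of an early-exit score as the endpoint. No shift in the primary result or loss of power is shown. Confidence is high that the sections conflict and lower that the conflict would change any reported result. Severity: minor.

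**What to change.** **Correct the status.**

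- In 18.3, state that subjects terminated before Visit 3 are counted as discontinued due to an adverse event and are not replaced.
- In 10.1, define completers by reference to 18.1, that is, Visit 3 completed. Do not add a Day 14 ± 2 condition: it could newly exclude subjects who attend Visit 3 outside the window.

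**Separately, for the completers-only rule in 10.1.** Add one supportive analysis of SANDE change by randomised arm in all subjects with any post-baseline score. Where Visit 3 is missing, use the 9.2.4 exit assessment or Visit 2, whichever is the last available. Label it supportive, and report by arm the number with no post-baseline score, since those subjects remain outside it.

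**Cost.** One clause in 18.3, one sentence in 10.1, and slightly more analysis work on data already collected. The supportive analysis will contain some off-window, carried-forward values. No visits or procedures are added, and the primary t-test and the clinical termination rule stay as planned. The changes should be made before unmasking, so that who completed is not decided with results in view.
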